In fact, about 10% of patients over 75 years of age who suffer a hip fracture die within 30 days of surgery at cause of intra- and post-operative complications that aggravate a general state of health already compromised by pre-existing comorbidities. In addition, the drastic change in life triggered by the severe disability caused by this fracture, which often leads to a substantial loss of autonomy, causes the 1-year mortality rate to rise between 14% and 36%.⁵ 42% of survivors do not return to pre-fracture mobility, 35% are unable to walk independently, 20% are unable to shop independently, and approximately 20% enter a long-term care facility during the first year after a fracture.⁴

In an attempt to lengthen the expectations and quality of life of these patients, the most recent guidelines suggest a multidisciplinary approach for the treatment of unstable hip fractures that involves, where possible, the close collaboration of different specialists such as the orthopedist, the geriatrician, the anesthesiologist, the cardiologist and the physiatrist. Although a consensus on the best possible treatment has not yet been found, several studies demonstrate a real benefit in the use of multidisciplinary protocols that always provide for timely surgical treatment of the fracture.^{5,6}

To date, there are several treatment options available for unstable hip fractures, each with advantages and disadvantages, including external fixation systems, internal fixation systems and partial or total hip replacement. In the field of internal fixation, the use of intramedullary nails has become increasingly popular due to the biomechanical advantages they provide in many indications compared to other synthetic media such as plates or dynamic cephalic screws.

However, the percentage of complications considered serious, i.e. requiring reoperation, associated with intramedullary nail treatment, such as cut-out, lateral protrusion of the cephalic screw and peri-implantation fractures, remains clinically significant (overall they can affect up to 30% of patients treated).

The *Chimaera* developed by Orthofix Srl is an intramedullary nail also indicated for the treatment of proximal femur fractures that integrates technical features specifically designed to decrease the probability of encountering the most serious and frequent complications in this type of treatment.

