9.4 Endpoint

In the present Clinical Investigation, the two variables chosen as *the primary and secondary endpoints* to measure the primary and secondary objectives of the Survey also coincide with the measures of response to treatment, in particular:

- Primary endpoint (security measure):

the safety of the *Chimaera* will be measured by the percentage of patients who within a 6-month observation period, due to serious adverse events related to *the Chimaera*, will have to undergo a second operation to continue with the treatment of the proximal femur fracture.

- Secondary endpoint (efficacy measure):

the effectiveness of the treatment carried out with *Chimaera* will be measured through the Bowers & Parker functional score for the evaluation of the patient's functional recovery.

Note:

Bowers & Parker's functional score⁷ It is a validated and unanimously recognized reliable score for the evaluation of patients treated following a hip fracture. This score assesses the patient's functional recovery (in terms of pain, walking ability and social independence) compared to the patient's condition before the fracture. The Bowers & Parker score also has predictive value for assessing the long-term mortality of the treated patient, and for planning short-term rehabilitation activities.

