9.5 Variables to measure

The primary endpoint (safety measure) of the present Clinical Investigation will be measured as follows:

- the correlation of the serious adverse event to the *Chimaera* will be freely assigned by the Investigator according to the following options: unrelated/potentially related/certainly related. Serious events potentially or certainly related to the *Chimaera* will be included in the calculation of the security measure.
- It is understood that, for serious events judged to be potentially or certainly related to the *Chimaera*, the Sponsor reserves the right to supplement the Investigator's assessment with an opinion from an independent orthopaedic physician and with a technical analysis of the implanted and removed device to proceed with the second intervention. Following these analyses, if the removed device complies with the design specifications, and if the independent orthopedist finds an operating technique error in the primary implant, in agreement with the Investigator, the event initially classified as potentially or certainly related to the *Chimaera* may be reclassified as unrelated and, therefore, will be excluded from the calculation of the safety measure. Similarly, serious adverse events due to use that does not comply with the manufacturer's instructions for use, otherwise referred to as *off label use*, will be excluded from the calculation of the safety measure.

The *secondary endpoint* (efficacy measure) of the present Clinical Investigation will be measured as follows:

- The Investigator will fill out a scale (Appendix 1) for each patient at each of the follow-up visits (1, 3, 6, and 12 months). If necessary, a translation of the scale into Italian is also provided to support comprehension.
- As suggested by the authors, the scale can be filled in by the Investigator on the basis of the answers provided by the patient, even by telephone. Given the type of patients that will be recruited, mostly non-self-sufficient elderly people who cannot always be moved easily, this procedure will not involve additional risks for the patient and should limit the number of patients that cannot be assessed due to lack of data on the secondary *endpoint*.

Data for the primary and secondary *endpoints* will be:

- reported in the patient's medical record and recorded in the electronic database provided free of charge by the Sponsor to each Investigator to collect the data of the Clinical Investigation;

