9.11 Medical-Surgical Procedures and Follow-up of the Clinical Investigation

After obtaining informed consent, the physician will include in the study those patients who, at the screening visit (Visit 0), meet all selection criteria. During the screening visit, the Investigator will also collect demographic data and the patient's medical history.

Enrolled patients, as would also occur if they chose not to participate in the present Investigation, will undergo the surgical procedure (Visit 1) required for the application of the investigational medical device (Chimaera), which marks the beginning of the treatment period.

Following the surgery, the patient will attend five subsequent visits. The first three visits after the surgical procedure are part of the treatment period and are:

- the visit performed at hospital discharge (Visit 2), which, unless complications occur, will take place within 10 days after the date of surgery. During this visit, the physician will perform routine assessments to confirm that the operation and postoperative course have proceeded appropriately;
- the following two visits (Visits 3 and 4), were conducted at 1 month and 3 months after the date of surgery, respectively. These visits conclude the treatment period which, in the absence of complications, is expected to be within 8–12 weeks from the date of surgery, with the consolidation of the treated proximal femoral fracture. Healing will be assessed by the Investigator through radiographic evaluation, performing a qualitative assessment of bone density at the fracture site and the alignment of the bone fragments. Starting from Visit 4 and at all subsequent visits, the Investigator will also complete the Bowers & Parker functional score (efficacy measure) to assess the patient's functional recovery.

For these patients, device removal is not planned unless required due to serious adverse events necessitating a second surgical procedure to complete the treatment of the fracture (safety measure). Once the treatment period is concluded, the follow-up period begins, during which two visits will be conducted (Visits 5 and 6), respectively at 6 months and 1 year after the date of surgery. During these visits, clinical data will be collected to monitor the progression of fracture consolidation, the patient's functional recovery, and the occurrence of any medium-term adverse events.

[figure not shown]

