9.14 Predictable factors that can compromise results

The procedures described in this Protocol are part of the normal clinical practice of the Centers involved. In fact, this clinical investigation is observational so it will not change the clinical protocols currently in use in the Centers involved, nor does it involve additional risks for patients and investigators.

In the present clinical investigation, given the type of patients who will be enrolled, two factors are known that could compromise the outcomes and the interpretation of the results, namely:

- For some very elderly patients who have difficulty moving and with impaired cognitive ability, for example due to senile dementia or advanced neurodegenerative diseases, the assessment of functional recovery may be more difficult.

The Bowers & Parker Functional Score⁷ chosen to assess the patient's functional recovery in terms of pain, walking ability and social independence, as described by the authors, precisely because it could be used in high probability on patients unable to answer reliably, it is composed of questions that can also be answered by the patient's companion (e.g. cohabitant, family member, caregiver, social health worker, etc.), understood as a person who lives in close contact with the patient. The companion can also answer by phone and, given the difficulty of moving this type of patient, this possibility will be very useful to limit the loss of data on the patient's functional recovery in the follow-up period.

- The mortality rate of enrolled patients is about 10% at 10 days after surgery and can reach up to 36% at 1 year. Therefore, a high percentage (25% on average) of non-assessable patients, i.e. discontinued before the end of the treatment period for supposed recovery (scheduled for the check-up visit in the third month after the operation), is expected in the present clinical investigation.

In order to increase the probability of reaching the expected sample size, i.e. 300 evaluable patients, i.e. who will complete at least the scheduled follow-up visit at the third month after the operation (Visit 4), the Sponsor has planned the enrollment of 400 patients and has agreed with the Investigators on a patient replacement procedure described below.

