The following table shows the number of patients and the upper limit of the confidence interval for different possible values of the percentage of the primary *endpoint* (calculations were made using the statistical method of the exact binomial):

Percentage of patients with second intervention	Upper limit of the 95% confidence interval	Number of patients observed
3%	8.518%	100
4%	9.926%	100
5%	9.614%	160
6%	9.703%	250
7%	9.958%	400

Based on the frequencies of serious device-related adverse events and/or device failures received by Orthofix Srl through the passive medical device vigilance system since the device was placed on the market, the expected percentage for the primary *endpoint* is no more than 6%. Therefore, the expected enrollment of 400 patients that will potentially allow us to obtain a sample of 300 evaluable patients is considered adequate for the type and objectives of the present clinical investigation.

The clinical data collected during this Clinical Survey will be analyzed through descriptive statistics:

- the *primary endpoint* will be presented as a percentage value and the corresponding 95% confidence interval;
- the *secondary endpoint* (Bowers & Parker functional score) and other radiographic parameters will be presented via quantitative descriptive statistics (mean, standard deviation, median, minimum, maximum, 95% confidence interval).

During the present Clinical Investigation, if necessary, an interim statistical analysis of the collected data could be carried out, e.g. when all patients have completed the third post-operative check-up (expected within 6 months from the date of operation).

The clinical data obtained from this Clinical Investigation will be used to complete the evaluation of the clinical performance and safety of the *Chimaera* in order to confirm that the device can be considered

effective and safe as assumed under development based on pre-clinical evaluations carried out for obtaining the CE mark.

19 Dissemination of results

The Investigators and the Sponsor undertake to keep the clinical data collected through this Clinical Investigation confidential and confidential until the information is made public in anonymized form by the Sponsor at the end of the Investigation.

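### Visit-by-visit summaries of the Bowers & Parker score cover only patients scored at each visit, so deaths among patients with worse scores can make later means look better with no individual improvement

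*Combined protocol and SAP*

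**What the plan says.** **Analysis.** Section 18 is the whole plan for the secondary endpoint: the score "will be presented via quantitative descriptive statistics (mean, standard deviation, median, minimum, maximum, 95% confidence interval". No section gives an analysis population for it, a rule for deaths or missing scores, or a change within patients.

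**Link to death.** Section 9.4 states: "The Bowers & Parker score also has predictive value for assessing the long-term mortality of the treated patient". Section 9.14 says that mortality "can reach up to 36% at 1 year". The background in Section 2 gives a range: loss of autonomy "causes the 1-year mortality rate to rise between 14% and 36" per cent.

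**Scale.** In Appendix 1 higher is worse on all three items (mobility 1 to 10, social dependence 1 to 8, pain 1 to 8). Pain also has a code 0 for patients for whom no answer can be obtained. No item has a value for death.

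**Who stays in.** Section 9.15 lists death among the reasons for early discontinuation. Section 9.14 calls a patient evaluable once the Month 3 visit is completed, so someone who dies later is evaluable but has no later score. Section 9.16 promises that data of discontinued patients will be analysed, without saying how.

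**Timing.** Section 9.11 says: "Starting from Visit 4 and at all subsequent visits, the Investigator will also complete the Bowers & Parker functional score". The table in Section 9.13 agrees (Months 3, 6 and 12). Section 9.5 instead has the scale completed "at each of the follow-up visits (1, 3, 6, and 12 months".

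**The concern.** Section 9.4 describes recovery relative to the patient's state before the fracture, but Section 9.13 schedules no score for that state. A reader who wants to see recovery has only the visit summaries to compare. Each can include only patients who were alive and scored at that visit. If those who die had worse scores, as Section 9.4 implies, their departure lowers the later means, and on this scale a lower mean reads as better function.

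This score is the only efficacy measure. The study has no control arm in which the same survivor effect would show up, and Section 18 intends to use the data to confirm that the device is effective and safe. The planned confidence interval does not reveal the problem, because it measures sampling error and not a change in who is being averaged.

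**Working it through.** **The plan's own figures.** The documents give no figure for the functional score. The only planning number used here is 300 evaluable patients, and it reproduces: 300 / (1 − 0.25) = 400 enrolled.

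**Step 1: identity.** Let q be the share of Month 3 patients who die by Month 12, and suppose that no patient's own score changes. Then

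mean of survivors − mean of all at Month 3 = −q × (mean of those who die − mean of survivors).

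The shift is zero only if the two groups have the same mean score.

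**Step 2: range of q.** With D3 and D12 the cumulative mortality at Months 3 and 12, q = (D12 − D3) / (1 − D3).

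- Low: 10% early (Section 9.14) and 14% at one year (Section 2): (0.14 − 0.10) / 0.90 = 4.4%.
- Middle: the whole 25% loss before Month 3 (Section 9.14) assumed to be death, and 36% at one year: (0.36 − 0.25) / 0.75 = 14.7%.
- High: 10% early and 36% at one year: (0.36 − 0.10) / 0.90 = 28.9%.

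The low and high cases assume no further deaths between the early period and Month 3.

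**Step 3: illustrative model.** Assumed, not from the documents: mobility mean 5.5 and SD 2.1 at Month 3, scores fixed thereafter, logistic risk of death with odds ratio (OR) 1.2 or 1.4 per point. As a yardstick, the 95% half-width of one visit mean is 1.96 × 2.1 / √300 = 0.24. The last column is 0.24 / q: how much worse those who die must score for the shift to equal the half-width.

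| q | alive at Month 12 of 300 | fall in mean, OR 1.2 | fall in mean, OR 1.4 | gap needed for a fall of 0.24 |
|---|---|---|---|---|
| 4.4% | 287 | 0.03 | 0.06 | 5.4 |
| 14.7% | 256 | 0.11 | 0.19 | 1.6 |
| 28.9% | 213 | 0.20 | 0.36 | 0.83 |

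These falls vary by about 0.02 with how a normal distribution is laid onto ten categories.

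**Step 4: hand check.** For a roughly normal score and uncommon deaths, the gap is close to ln(OR) × SD². This is 0.182 × 4.41 = 0.80 for OR 1.2 and 0.336 × 4.41 = 1.48 for OR 1.4. Multiplying by q gives 0.04 and 0.07, 0.12 and 0.22, 0.23 and 0.43. These are slightly above the table, as expected, because the real scale is bounded and deaths are not rare in the high case.

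**Step 5: other assumed values.** With mean 5.0, SD 2.35 and odds ratios of 1.1, 1.2, 1.3 and 1.5, the fall is 0.08, 0.15, 0.21 and 0.30 at q = 14.7%, and 0.15, 0.28, 0.40 and 0.57 at q = 28.9%. At q = 4.4% the largest is 0.09. The half-width is then about 0.27 (SD 2.4, n = 300).

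**The case against.** The strongest reply is that the plan is descriptive. Section 18 tests no hypothesis, sets no threshold and specifies no comparison of Month 3 with Month 12. A mean over patients alive at a visit is a legitimate description of those patients. This stands, so the fault is not a wrong test. It is that the plan offers nothing else from which recovery could be read, while Section 9.11 says the later visits serve to monitor functional recovery.

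A reader might infer that deaths are bound to make function appear to improve. The documents do not support that:

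- Survivor-only means are inferred from the plan's silence and from a scale with no value for death; they are not written down.
- Section 9.4 gives neither the strength of the link with mortality nor a 12-month horizon, and it implies the direction without stating it.
- Real decline in survivors could cancel or reverse the shift.
- Most of the illustrated shifts are below the half-width.
- Mobility alone was modelled. If pain code 0 is averaged as a number and such patients die more often (an assumption), their loss would raise the pain mean, which would look like worsening.

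Proxy and telephone answers (Sections 9.5 and 9.14) do reduce missing scores in living patients, but they do nothing about deaths.

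**Conclusion.** The point holds as a possible bias in how the score will be read, and it merits a change to Section 18. The mechanism follows from the protocol's own statements, if worse scores go with higher mortality. The size does not: it runs from negligible when few die after Month 3 to more than the 95% half-width when late mortality is high and the link with death is strong. The mean, SD and odds ratios are assumptions, and the mortality range is read from Sections 2 and 9.14. Only deaths after the first scored visit affect the trend; earlier deaths affect whom the first mean represents.

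It would go too far to say that the planned efficacy result will be spuriously favourable, or that the safety conclusion is touched. The primary endpoint and the sample size are unaffected.

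**What to change.** In Section 18, keep the visit summaries and add:

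1. Within-patient change between visits, in patients scored at both, labelled as describing survivors only. This removes the effect of changing membership but not the restriction to survivors.
2. At each visit, the distribution of each item over all implanted patients, with 'died' and 'not assessed' as separate categories. Pain code 0 counts as not assessed and does not enter a mean.
3. A statement that differences between visit means are not interpreted as recovery.

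Reconcile the scoring times in Section 9.5 (from Month 1) with Sections 9.11 and 9.13 (from Month 3), since they determine which visit starts the comparison.

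The cost is two extra descriptive tables from data already planned for collection. These tables do not supply the pre-fracture comparison described in Section 9.4, because no such score is scheduled.

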Appendix 1: Bowers & Park Scale

Mobility (select the appropriate condition using the left column) A score of one represents a patient who has no need for any walking aid and has no restriction in walking distance, through to 10, which represents a bedbound individual.		
1	Never uses any walking aid and no restriction in walking distance.	
2	Never uses any walking aid, but walking distance limited to less than one kilometre.	
3	Occasionally uses a walking aid when out walking.	
4	Normally uses one walking stick or needs to hold on to furniture.	
5	Normally uses two sticks or crutches.	
6	Mobilises with a frame alone, without the need for assistance.	
7	Mobilises with a frame and the assistance of one other person.	
8	Mobilises with a frame and the assistance of two people.	
9	Bed to chair (with or without assistance), or wheelchairbound.	
10	Bedbound most or all of the day.	

Social dependence (select the appropriate condition using the left column) Give a value of one for a person who is completely independent and living at home not requiring any support or assistance, to eight which is a fully dependant requiring patient requiring care in hospital		
1	Completely independent. Requires no assistance in basic or advanced activities of daily living (ADL) including shopping.	
2	Minimal assistance. Requires occasional help up to twice a week from family, friends or other services with some activities such as shopping or gardening.	
3	Moderate assistance. Requires regular assistance more than twice a week but less than seven times a week with some ADL such as bathing, washing or heavy housework.	
4	Regular assistance. Requires daily help to assist with ADL.	
5	Dependent. Requires regular help more than once a day with many basic ADL such as preparing food and housework but remains living at home.	
6	Severely dependent. Living in residential care. Full-time care facility but independent of at least one basic ADL such as being able to dress or go to the toilet without help.	
7	Fully dependent. Living in nursing home, skilled nursing home or long-term hospital facility with full-time nursing care. Patient requires assistance in most ADL living such as washing, dressing and getting to the toilet.	

	8	Patient temporarily resident in hospital requiring both nursing and medical care.
--	---	---

Pain (select the appropriate condition using the left column)

A score of zero is given if the patient or their attendant carer is unable to answer, else the pain is rated one (no pain in the hip) to eight (constant and severe pain requiring regular strong analgesia).

0	Unable to answer.
1	No pain at all in the hip.
2	Occasional and slight pain. May occasionally take mild analgesia such as paracetamol.
3	Some pain when starting to walk, no rest pain. Occasional analgesia taken.
4	None or minimal pain at rest, some pain with activities, frequent mild analgesia.
5	Regular pain with activities which limits walking distance. Occasional or mild rest pain.
6	Frequent rest pain and pain at night. Pain on walking. Regular mild analgesia and occasional stronger analgesia taken.
7	Constant pain present around the hip. Regular mild analgesia and frequent strong analgesia.
8	Constant and severe pain in the hip requiring regular strong analgesia such as opiates.
